#### **6.11.5 Physical Examination**

The investigator, sub-investigator or appropriately delegated designee will perform a physical examination, prior to the Subject starting study drug and at the end of treatment. The physical examination will include, at a minimum, examination of the Subject's general appearance, comprehensive skin examination, HEENT (head, eyes, ears, nose and throat), heart, lungs, musculoskeletal system, neurological system, lymph nodes, abdomen and extremities.

Each body system will be classified as normal, abnormal not clinically significant or abnormal clinically significant.

Number and percentage of subjects with normal, abnormal not clinically significant or abnormal clinically significant findings will be presented by body system, visit and treatment group.

All results will be listed.

#### **6.11.6 Prior and Concomitant Medication**

Prior and concomitant medication will be coded according to the World Health Organization – Drug Dictionary version MAR 01, 2022 and the Anatomical Therapeutic Chemical (ATC) classification system. Prior medications are defined as those taken before the first dose of the study drug (i.e., start and end date before the first dose of the study drug). Concomitant medications are defined as those taken at the time of or after the first dose of the study drug. Any medications that were started before the first dose of the study drug but continued after dosing will be considered a concomitant medication.

Medications concomitant with Part I will be defined as those taken at any time on or after the first study drug dose date in Part I and prior to the first study drug dose date in Part II. Medications concomitant with Part II/III/IV will be defined as those taken at any time on or after the first study drug dose in Part II.

All previous and concomitant medication will be listed by subject. Concomitant medications in Part I, in Parts II/III/IV and in the study overall will be summarized by treatment group, ATC class (highest level available) and preferred name. The summary for the study overall will include only subjects staying on the same treatment throughout the study. This analysis will be done for the Safety population.

All prior and concomitant medications will be listed.

#### **6.11.7 Pulmonary Function Tests**

At the study Visits 1 and 19 (Screening and study Week 52) pulmonary function tests (PFTs) will be performed, including assessment of FEV1 and FVC. Spirometry will be performed in accordance with American Thoracic Society standards. The results will be compared to the predicted values based on factors such as age, gender, and ethnicity

Additional pulmonary assessments will be done in case of clinically significant abnormal findings on the PFTs or physical examination and at the discretion of the Investigator in subjects with respiratory complaints like dyspnea, shortness of breath, chest tightness, wheezing etc.

Spirometry parameters such as FEV1, FEV1 Percent Predicted, FVC, FVC Percent Predicted and FEV1/FVC Ratio as well as their changes from baseline to Week 52 will be summarized descriptively by visit.

## 7. TIMING OF ANALYSES

### 7.1 Interim Analysis of Cardiac Safety

An unblinded analysis of the cardiac safety data will be performed by an unblinded study team after approximately 50 subjects complete the initial [REDACTED] period. The duration of in-clinic cardiac monitoring after first dose and/or certain dose escalation visits may be increased up to 24 hours if this review indicates new onset cardiac rhythm abnormalities after 6 hours of dosing that justify monitoring beyond 6 hours. Based on ongoing safety review by the Independent Safety assessor and Independent MM, recruitment of subjects may continue during review of cardiac monitoring results from these initial subjects.

A subset of tables and listings identified in a separate “Cardiac Safety Data Analysis Shell” document will be prepared. This analysis will include only the data from Part I of the study, i.e. findings collected and events starting up to the date of Week 16 visit of each subject.

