7.1.6 On-site Visit 10: Visit [REDACTED]

The visit 10 must be scheduled in a morning to allow the dosing before 12 noon.

The following procedures will be performed at Visit 10:

1. Subject Reported Assessments will be collected for:
 - Dermatology Life Quality Index (DLQI) (See Section 6.1.1)
 - Psoriasis Symptoms and Signs Diary (PSSD) (See Section 6.1.2)
 - Patient Global Impression of Severity (PGIS) (See Section 6.1.3)
 - Patient Global Impression of Change (PGIC) (See Section 6.1.4)
 - Itch Numeric Rating Scale (itch NRS) (See Section 6.1.5)
 - Scalp Itch Numeric Rating Scale (scalp itch NRS) – *for subjects with Scalp psoriasis* (See Section 6.1.6)
 - Health Assessment Questionnaire of disability (HAQ-DI) – *for subjects with PsA* (See Section 6.1.7)
 - Patient Global Assessment of Disease Activity (PtGA) – *for subjects with PsA* (See Section 6.1.8)
 - Patient Assessment of Pain (PtA-P) – *for subjects with PsA* (See Section 6.1.9)
2. Focused Area Assessments will be performed for:
 - Investigator's Global Assessment (IGA) (See Section 6.1.10)
 - Scalp Investigator's Global Assessment (Scalp IGA) – *for subjects with Scalp psoriasis* (See Section 6.1.11)
 - Palmoplantar Physician Global Assessment (PPPGA) – *for subjects with Palmoplantar Psoriasis* (See Section 6.1.12)
 - Psoriasis Area Severity Index (PASI) (See Section 6.1.13)
 - Body Surface Area (BSA) (See Section 6.1.14)
 - modified Nail Psoriasis Severity Index (mNAPSI) – *for subjects with Nail psoriasis*

Following will be assessed by an independent assessor (See Section 6.1.15)

- Tender and Swollen Joint Count – *for subjects with PsA* (See Section 6.1.17)
- Physician Global Assessment of Disease Activity (PGA) – *for subjects with PsA* (See Section 6.1.18)

3. A urine pregnancy test will be conducted for all females of childbearing potential (see Section 5.4)
4. IRT system consulted for re-randomization and selection of kit
5. A whole body photography – *for subjects consenting for photography* (See Section 6.4)

The following procedures will be performed by an independent safety team:

6. Vital signs (blood pressure, pulse, respiratory rate and oral body temperature) will be documented. Subjects must remain in a seated or supine position for at least 5 minutes before vital signs are obtained. (See Section 5.3)
7. The occurrence of all AEs & AESIs will be assessed and documented following the procedures in Sections 5.9, 10.1, and 10.3.

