8. A query for PML (progressive multifocal leukoencephalopathy) will be performed (See Section 5.10)
9. A query for PRES (Posterior reversible encephalopathy syndrome) will be performed (See Section 5.11)
10. The Subject's body weight will be measured while the Subject is lightly clothed (e.g., no coat or shoes)
11. The Subject's diary provided at the previous visit will be collected and reviewed.
12. The returned study drugs will be counted
13. The use of concomitant medications since the previous study visit will be documented and assessed. (See Section 5.8)
14. A urinalysis dipstick will be performed and evaluated at a site (See Section 5.5)
15. A blood sample will be collected for Hematology, Lipid Profile, Chemistry, and Coagulation profile (See Section 5.5)
16. A blood sample will be collected for PD biomarkers sample (See Section 6.3)
17. A blood sample will be collected within one hour before dosing for PK testing (See Section 6.2)
18. A blood sample will be collected for C-reactive protein (CRP) – (See Section 5.5)
19. Independent Safety Assessor review:
 - Safety Lab Alerts
 - [REDACTED]
 - As available
 - i. Lab results
 - ii. Exam results
20. Study drug administration in a clinic before 12 noon (See Section 8.5)
21. [REDACTED]
[REDACTED]
[REDACTED]
22. A general safety review before discharge
23. On-site Visit 14 (Study Day 134 ±1 Day) will be scheduled and the Subject will be instructed to bring the Study Product (used, unused, and partially used packs), and Subject diary with him or her to this visit.
24. [REDACTED]
[REDACTED]
[REDACTED]

■ [REDACTED]
■ [REDACTED]
■ [REDACTED]

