### **6.1.1 Treatment Groups**

Data collected up to Week 16 visit will be analyzed by treatment groups based on the subject’s treatment in Part I of the study:

- Placebo

- SCD-044 [REDACTED]
- SCD-044 [REDACTED]
- SCD-044 [REDACTED]

Efficacy data collected after Week 16 visit (i.e., Parts II-IV), as well as disposition and compliance in Parts II-IV, will be analyzed by treatment groups based on the responder status at the end of Part I (Week 16) (i.e.,  $\geq$  PASI50 or  $<$  PASI50), the subject's treatment in Part I and the subject's treatment in Part II of the study:

- Part I Responders
  - Placebo/SCD-044 [REDACTED]
  - Placebo/SCD-044 [REDACTED]
  - SCD-044 [REDACTED]
  - SCD-044 [REDACTED]
  - SCD-044 [REDACTED]
- Part I Non-Responders
  - Placebo/SCD-044 [REDACTED]
  - Placebo/SCD-044 [REDACTED]
  - SCD-044 [REDACTED]
  - SCD-044 [REDACTED]

Safety data collected after Week 16 visit (i.e., Parts II-IV) will be analyzed by treatment groups based on the subject's treatments in Part I and in Part II:

- Placebo/SCD-044 [REDACTED]
- Placebo/SCD-044 [REDACTED]
- SCD-044 [REDACTED]

Adverse events and concomitant medications will be additionally analyzed for the entire study. Details are provided in the sections 6.11.1 and 6.11.6.

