### **6.11.1 Adverse Events**

Adverse events will be coded using MedDRA, Version 25.0, AE coding system for purposes of summarization.

An AE will be considered as treatment-emergent (TEAE) if the date of onset is on or after the date of the first study drug administration. AEs with unknown start dates will be counted as treatment-emergent unless the AE resolution date is prior to the study drug start date. If the start date is partially missing, the AE will be considered treatment-emergent, unless the month and year (when available) rule out the possibility that the event occurred post start of study drug dosing.

A TEAE is defined as treatment-related if its relationship to study medication is recorded as “Possible”, “Probable” or “Definite” on the eCRF. In case the relatedness was not assessed, the most conservative result (related) will be chosen for the analysis.

Cardiovascular AEs will be defined as AEs with MedDRA system organ class “Cardiac disorders” or “Vascular disorders”.

Adverse events that are of special interest, that represent signs/symptoms of Progressive Multifocal Leukoencephalopathy (PML) or of Posterior Reversible Encephalopathy Syndrome (PRES) and that are cardiac arrhythmias will be marked on the eCRF.

AEs will be assigned to Part I or Parts II/III of the study based on the date of onset, i.e. AEs that start prior to the first dose of the Part II treatment will be assigned to the Part I and AEs that start on or after the date of the first Part II dose will be assigned to the Parts II/III. In case AE start date is partially known so that there exists an ambiguity whether the AE starts in Part I or Part II, it will be assigned to Part I.

In summaries of TEAEs a subject experiencing the same AE multiple times on the same treatment will only be counted once for that preferred term and treatment. Similarly, if a subject experiences multiple AEs within the same system organ class on the same treatment that subject will be counted only once in that system organ class and treatment. When summarizing AEs by severity, only the most severe occurrence within the preferred term or system organ class and treatment will be used. Similarly, when summarizing AEs by relationship to study drug, only the most related occurrence within the preferred term or system organ class and treatment will be selected for displays in summary tables.

All AE summaries will be presented in 3 ways:

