The tables for the [REDACTED] periods will be separated into sections for Week 1, Week 2 and Week 3 of [REDACTED] where the weeks are defined by the dates of the [REDACTED] visits (Week 1, Week 2 and Week 3 for Part I and Week 16, Week 17 and Week 18 for Part II). Only events occurring in each week in the treatment groups still undergoing [REDACTED] (including the Placebo group in Part I) will be included. In the Part II table five columns will be included: Placebo/SCD-044 [REDACTED] Placebo/SCD-044 [REDACTED] SCD-044 [REDACTED] SCD-044 [REDACTED] and Total as only these groups actually undergo [REDACTED] in Part II.

All information pertaining to adverse events noted during the study will be listed by subject, detailing verbatim, preferred term, system organ class, start date and study day, stop date, intensity, outcome, action taken and causal relationship to the study drug. The adverse event onset will also be shown relative (in number of days) to the date of first administration of the study drug.

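### SAP 7.1 and 6.1.1 end Part I at the Week 16 visit, other SAP rules at the first Part II dose given at that visit, so switchers' post-dose cardiac findings that day can be counted under Placebo or the old dose

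*SAP*

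**What the plan says.** Two SAP sections cut Part I at the visit. Section 7.1 (Interim Analysis of Cardiac Safety) restricts the interim to Part I, which it explains as "findings collected and events starting up to the date of Week 16 visit of each subject". The interim is run "after approximately 50 subjects complete the initial" period (the name of the period is blacked out). Section 6.1.1 (Treatment Groups) gives the general rule: "Data collected up to Week 16 visit will be analyzed by treatment groups based on the" Part I treatment of the subject. It then sends only safety data from after that visit to the groups defined by Part I and Part II treatment together.

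Three SAP rules cut at the first Part II dose. Section 6.11.1 (Adverse Events) says that "AEs that start on or after the date of the first Part II dose will be assigned to the Parts II/III". Section 6.1 takes the Part II baseline as the last assessment before the first Part II dose. Section 6.11.6 divides concomitant medication at the date of that dose.

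Protocol 7.1.6 (On-site Visit 10, which is Week 16) lists "IRT system consulted for re-randomization and selection of kit" as item 4, a pre-dose PK sample as item 17, and "Study drug administration in a clinic before 12 noon" as item 20. SAP 6.11.1 defines the weeks of its early-treatment tables by "Week 16, Week 17 and Week 18 for Part II".

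**The concern.** Bradyarrhythmia and AV conduction delay head the list of class risks in protocol 4.6, and they are looked for after the first dose of a new regimen. Every placebo group that SAP 6.1.1 carries beyond Week 16 moves to SCD-044. For those subjects the Week 16 dose is the first active dose. Low- and intermediate-dose subjects who switch also take a new regimen from that day.

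Part I is the only placebo-controlled part of the study, and SAP 7.3 produces all Part I tables once the last subject has passed Week 16. The extended-monitoring text after SAP 6.11.8 (its heading is missing from the public copy) rests on pulse and ECG six hours after a dose. It reports by treatment group, by visit and over all visits combined. If Week 16 post-dose records go to the Part I column, a reaction to SCD-044 can appear as a finding on Placebo, or a reaction to the high dose as a finding on a lower one.

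**Working it through.** The documents state no figure that depends on this boundary, so there is nothing to reproduce. The check is a comparison of rules, followed by a note on scale.

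**Step 1: when is the first Part II dose?** At Visit 10, re-randomisation (item 4) and the pre-dose PK sample (item 17) come before the in-clinic dose (item 20). SAP 6.11.1 counts Week 16 as the first Part II week. For a switcher, the date of the first Part II dose is therefore the Week 16 visit date.

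**Step 2: where does each rule put a switcher's record from after that dose, on that day?**

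| SAP rule | Boundary | Result |
|---|---|---|
| 7.1, cardiac interim | Week 16 visit date | Part I, if the date is included |
| 6.1.1, general rule | Week 16 visit | Part I treatment |
| 6.11.1, adverse events | Date of first Part II dose | Parts II/III |
| 6.1, Part II baseline | First Part II dose | After the Part II baseline |
| 6.11.6, concomitant medication | Date of first Part II dose | Parts II/III/IV |

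The first two rows disagree with the last three. An event starting that day is in Part I under 7.1 and in Parts II/III under 6.11.1.

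**Step 3: does the visit-based wording include the visit?** For 6.1.1 it must. The primary endpoint is PASI75 at Week 16, assessed at this visit and compared between Part I groups. SAP 6.8.3.5 also states that Part I includes the Week 16 visit. For 7.1 the cut is a calendar date, which cannot separate pre-dose from post-dose records. Included, the date brings in post-dose findings. Excluded, it drops valid pre-dose ones.

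**Step 4: scale, on assumed rates only.** Arm size is 240/4 = 60. The interim set holds about 50/4 = 12.5 placebo subjects. If n placebo subjects take a first active dose on the boundary date and each has a finding with probability p, the chance of at least one misplaced finding is 1 - (1 - p)^n.

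| n | p = 1% | p = 2% | p = 5% | p = 10% |
|---|---|---|---|---|
| 12 | 0.114 | 0.215 | 0.460 | 0.718 |
| 13 | 0.122 | 0.231 | 0.487 | 0.746 |
| 60 | 0.453 | 0.702 | 0.954 | 0.998 |

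These n are ceilings: 12 or 13 for the interim and 60 for the whole trial, reached only if every placebo subject arrives at Week 16 and switches. In the interim the true number could be 0, because the trigger is completion of the initial period.

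The direction for an any-visit summary follows from: Placebo rate = b + (1 - b) x s x a. Here b is the rate on placebo, a the first-dose rate on SCD-044, and s the share of placebo subjects who switch. With b = 3%, a = 10% and s = 50% (all assumed), the result is 0.03 + 0.97 x 0.5 x 0.10 = 0.0785, against a true 3%. With s = 80% it is 0.1076, and with s = 90% it is 0.1173.

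With the boundary at the first Part II dose, no post-dose finding on a new treatment falls in Part I.

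**The case against.** The best defence is that the intention is clear. SAP 6.1.1 glosses the later data as Parts II to IV, and three operational rules in the SAP use the first Part II dose. The surviving ECG text uses the Part II baseline for groups that switch, which fits a dose-based split. Most of the vital-sign and ECG sections and item 21 of Visit 10, directly after dosing, are blacked out or missing, so a local rule may exist there. Safety is descriptive; protocol 9.7 plans no inferential analysis. The interim asks whether rhythm abnormalities after six hours justify longer monitoring, and states no drug-placebo criterion.

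Much of this stands. The 6.11.1 tables, including those for cardiac arrhythmias, are protected apart from partial dates that leave the Part unclear, which default to Part I. Subjects who keep their dose are unaffected, as are by-visit summaries of Day 1. The hidden text cannot be judged. What does not stand is the claim that the wording is merely open: 6.1.1 has to include the Week 16 visit, and it gives the later groups only what comes after it.

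A reader might go further and infer that the SAP will count these findings under Placebo, and that a true excess on drug would vanish. With a = 10%, b = 3% and s = 80% to 90%, the formula puts Placebo at 10.8% to 11.7%, level with or above 10%. The documents do not support that inference. The rates are assumptions. SAP 6.2 shows that some non-responders are randomised to be discontinued after Part I, so s of 80% to 90% is an upper scenario. The comparison sets an any-visit placebo rate against a single first-dose active rate. It also leaves out low- and intermediate-dose switchers, whose Week 16 findings would enter active columns.

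**Conclusion.** The SAP contains two boundaries between Part I and Part II that disagree on the day of the switch. Taken literally, 6.1.1 and 7.1 allow Week 16 post-dose pulse, ECG and extended-monitoring findings in switchers to be tabulated under Placebo or the old dose, and 7.1 places a same-day event differently from 6.11.1.

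The effect is confined to subjects who switch, to findings other than adverse events, and to the outputs of 7.1. It matters more for the Part I tables of SAP 7.3 than for the interim. The direction is dilution of drug-placebo cardiac contrasts wherever Part I findings are pooled over visits. The amount cannot be derived: the documents give neither the first-dose rate nor the number who will switch. The conclusion assumes that the blacked-out vital-sign and ECG text holds no separate rule for Week 16 post-dose records. If it does, the conflict with 6.1.1 and 7.1 still needs to be resolved in the text. This should be corrected before the Part I tables are produced.

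**What to change.** State one boundary, the first Part II dose, in SAP 6.1.1 and 7.1 and in the vital-sign, ECG and extended-monitoring summaries. Week 16 pre-dose data go to Part I. Week 16 post-dose findings in switchers go to the Part I/Part II treatment group. Adverse events stay as 6.11.1 assigns them, and the events clause of 7.1 is reworded to match.

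The cost is SAP wording and a pre-/post-dose flag on Week 16 records. The extended-monitoring criteria already compare with the same day's pre-dose value, so the distinction should be available without new data.

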### 7.2 DSBM Review of Cardiac Safety Data

An independent DSMB will review treatment initiation cardiac monitoring results from approximately first half of the randomized subjects and provide a recommendation if the cardiac monitoring in subsequent subjects could be reduced, for example, to assessment of only pre-dose ECGs.

The outputs required for DSMB are described in the DSMB charter. These outputs will be prepared both in the blinded and unblinded fashion. Unblinded output will be created by a separate unblinded team. Initially the DSMB will review the blinded outputs, and then unblinded if required.

### 7.3 Part I Analysis

Once the last subject completes Week 16 visit (or early termination prior to Week 16), the analysis will be conducted on all available data to evaluate the primary and key secondary efficacy outcomes. At this time all planned tables, listing and figures pertaining to Part I of the study will be created. This will be the final analysis for the primary efficacy endpoint. Investigational sites, subjects, and study team members directly involved in study activities will remain blinded to study treatment assignments until the last subject completes the follow-up period (Week 56). A separate document, The Blinding Maintenance and Communication Plan will provide further details related to unblinding of personnel involved in reporting activities

#### **7.4 Final Analysis**

When all subjects complete the study, the final analysis will be performed. At this time the randomization code will be released and the statistical and programming team that was blinded throughout the study will become unblinded. For the final analysis all planned tables, listings and figures will be created.

### **8. CHANGES FROM PROTOCOL SPECIFIED ANALYSES**

Handling of intercurrent events is expanded in this SAP.

The endpoint of achieving DLQI score of 0 or 1 was added.

There are no other changes from the protocol-specified analyses.

## **9. LIST OF PLANNED TABLES, FIGURES, AND LISTINGS**

See separate document with the table, figure and listing shells.

